10.3. Populations for Analyses

For purposes of analysis, the following populations are defined:

Population	Description
All Subjects	All participants who receive at least 1 dose of study treatment and will be the population for reporting of safety and study population data. Participants will be analyzed according to the treatment they actually received.
РК	Participants in the 'All Subjects Population' for whom a PK sample was obtained and analysed and will be the population for reporting of PK data.

10.4. Statistical Analyses

10.4.1. Pharmacokinetic Analyses

All PK analyses will be performed on the PK Population.

For both parts of the study, plasma GSK2982772 concentration-time data will be analysed by non-compartmental methods.

The plasma concentration-time data for each of the regimens, the following PK parameters will be determined, as data permit:

- maximum observed plasma concentration (C_{max}).
- time to C_{max} (T_{max}).
- the elapsed time from dosing at which GSK2982772 was first quantifiable in a concentration vs time profile (T_{lag}).
- observed concentration at 24 hours post-dose (C_{24h}).
- observed concentration at 8 and 12 hours post-dose (C_{8h} and C_{12h}) for IR only.
- area under the plasma concentration vs time curve (AUC_(0-t), AUC₍₀₋₂₄₎ and AUC_(0-inf)).
- the percentage of AUC extrapolated beyond the last measured time point (AUC%extrap).
- terminal half-life $(t_{1/2})$.
- relative bioavailability (Frel_{formulation}) of test formulations (under fed or fasted conditions) vs reference formulation based on AUC₍₀₋₂₄₎ and AUC_(0-inf) (or AUC_(0-t) if AUC_(0-inf) can't be derived) and C_{max}.
- relative bioavailability (Frel_{FE}) of fed (high-fat breakfast or high-fat evening meal, standard breakfast or standard evening meal or delayed meal (30 or 60 minutes) vs fasted based on AUC and C_{max}.
- relative bioavailability (Frel(time effect) of evening dosing vs morning dosing based on AUC and C_{max})
- relative bioavailability (Frel_{MRFormulation}) of MR prototype coated tablet formulations relative to each other, as appropriate, based on AUC and C_{max} (optional Part B only)
- C_{max}/Dose and AUC/Dose (optional Part B only)

Descriptive statistics (n, arithmetic mean, standard deviation [SD], 95% CI, minimum, median and maximum) will be calculated by treatment for all PK concentrations over time and for the derived PK parameters. In addition, for log_e-transformed PK parameter variables geometric mean, 95% CI and %CV_b (100 * $\sqrt{(exp(SD2) - 1)}$) will be provided, where the SD is the standard deviation of log-transformed data.

Endpoint	Statistical Analysis Methods
Primary	The primary PK endpoints to compare MR formulations with IR formulations will be summarised descriptively. Ratios of $AUC_{(0-inf)}$, $AUC_{(0-24)}$, $(AUC_{(0-t)}$, if $AUC_{(0-inf)}$ cannot be derived), C_{max} , C_{24h} for MR formulation to IR formulation will be computed with 90% CI.
Primary	The primary endpoints for food effect will be summarised descriptively. In addition, log-transformed AUC _(0-inf) (AUC _(0-t) , if AUC _(0-inf) cannot be derived), C _{24h} , and C _{max} will be analysed using a mixed effects model with regimen as a fixed effect and subject within sequence as a random effect. Point estimates and corresponding 90% CI will

Endpoint	Statistical Analysis Methods
	be computed for the differences in GSK2982772 MR formulation taken in the fed state (test) vs in the fasted state (reference) using the residual error from the model (MSE). The point and interval estimates on the log-scale will then be exponentially back transformed to give estimates of the ratios of geometric means and 90% CI.
	Within-subject coefficients of variation for $AUC_{(0-inf)}$ and C_{max} will be calculated based on the log _e -Normal distribution: CV_w (%) = sqrt[exp(mse) - 1] x 100, where MSE is the residual error from the model.
	Statistical analysis of the PK endpoint T_{max} of GSK2982772 MR formulation administered under both fed and fasted conditions will be separately analysed non- parametrically [Hauschke, 1990]. The point estimates for the medians for each treatment, the median difference and 90% CI for the median difference will be calculated for the contrast (test-reference).
Secondary	The secondary PK endpoints for the selected MR formulations at different tablet strengths and multiple dose units will be summarised descriptively.
	For Part B, plots of dose vs dose normalised AUC ₍₀₋₂₄₎ , C_{24h} and C_{max} will be generated to determine if there are any dose dependent changes in the absorption of GSK2982772 following administration of different tablet strengths and multiple dose units of the selected MR formulation(s).
	For Part B, dose proportionality will be assessed by visual inspection of dose normalised AUC ₍₀₋₂₄₎ , AUC _(0-inf) [or if not available AUC _(0-t)] and C _{max} values versus dose. Analysis of these log _e -transformed parameters may be carried out, using the power model.
	For Part B Period 7, the relative bioavailability of time effect (Frel(time effect)) will be assessed by comparing $AUC_{(0-inf)}$, $AUC_{(0-t)}$, C_{max} , T_{max} , between evening dosing (test) versus morning dosing in the same prandial state (reference).

The Reporting and Analysis Plan will describe the planned PK analyses in greater detail.

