•	To assess the impact of evening dosing (Optional Part B, Period 7 only) on the PK of GSK2982772 following single dose administration selected GSK2982772 MR prototype coated tablet formulations.	•	GSK2982772 AUC _(0-inf) , AUC _(0-t) , C_{max} , T_{max} and $t_{1/2}$, relative bioavailability (Frel (time effect), based on AUC and C_{max}

Overall Design:

This is an open label, non-randomised single centre, two part, single dose study in healthy male and female participants to assess MR prototype coated tablet formulations of GSK2982772. The impact of food (high-fat breakfast) on the rate and extent of absorption will be evaluated for suitable MR prototype coated tablet formulations, and an assessment of alternative tablet strengths, dosing of multiple dose units and presence/absence of apertures in the tablet may also be performed. An assessment of a standard or high-fat breakfast/evening meal or study drug administration 30 or 60 minutes before a standard or high-fat (Part B, Period 7 only) breakfast or evening meal may also be included. The single dose may be given in the morning or evening (Part B, Period 7 only).

Part A of the study is a non-randomised up to 6 period, 6-way fixed sequence design in which up to 4 MR prototype coated tablet formulations may be evaluated following single dose administration in the fasted state (240 mg). Periods 1, 2 and 3 will evaluate MR1 (similar in vitro dissolution to the slowest minitab MR formulation from study 205017), IR tablet (240 mg) and MR2 (slower in vitro dissolution than MR1) respectively. Periods 4, 5 and 6 will be flexible and the dosing regimen will be dependent on the outcome of Periods 1 to 3. In Periods 4 to 6, there will be the option to optimise the MR release duration and evaluate the impact of a high-fat meal on one or more

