5.1.2. Part B

Optional Part B of the study is an open-label, non-randomised up to 7-period fixed sequence study design to evaluate the selected MR prototype coated tablet formulation(s) at different tablet strengths or as multiple unit doses and with or without apertures in the tablet coatings (Figure 2). Up to 4 different MR prototype coated tablet formulations may be selected for investigation in Part B. These will be selected from Part A and ongoing interim reviews in Part B; the selected formulations may be adjusted during interim reviews in Part B. The tablet strengths and the number of dosing units selected in Part B will be based on the exposure of GSK2982772 achieved in an ongoing high dose PK study in which doses of the IR tablet up to 240 mg TID are being administered, and the bioavailability of the selected MR prototype coated tablet formulations relative to the IR tablet (from Part A). Up to 4 different dose levels (as different tablet strengths or multiple unit doses) may be administered in Part B. The proposed dose levels are 120 mg, 480 mg, 960 mg and 1200 mg but these may be adjusted following review of the data from Part A or following the interim reviews during Part B, as appropriate. In Part B, administration of the MR prototype coated tablet formulations will either be in the fed or fasted state, or administered 30 or 60 minutes before a standard or high-fat (Period 7 only) breakfast/evening meal (Period 7 only), which will be based on emerging PK data. There will be an interim review following each of Periods 1 to 5 of Part B to select the dose level, formulation and prandial status, as appropriate, for each subsequent period. An interim data review after Part B Period 6 will determine if optional Period 7 is required and the dose level, dosing time (morning or evening), formulation and prandial status for that period.

Participants will be admitted to the clinic in the morning of the day before dosing (i.e., Day -1) of each inpatient period. Each inpatient period will consist of a 4-day, 3-night

inpatient period with a minimum of 7 days washout between doses. A follow-up visit will occur at 7 to 9 days after the last study treatment.
*

CONFIDENTIAL

Interim decisions based on PK and safety data. Periods 2 to 7 are flexible and the dosing regimen will be dependent on the outcome of the preceding periods.

¹ Proposed dose levels that may be adjusted following review of the data from Part A

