7.1.2. Treatments Administered - Part B

Regimen	G	Н	I (Optional)	J (Optional)	K (Optional)	L	M (Optional)
Study Treatment Name:	GSK2982772	GSK2982772	GSK2982772	GSK2982772	GSK2982772	GSK2982772	GSK2982772
Dosage formulation:	MR prototype Coated Tablet MRX	MR prototype Coated Tablet MRX	MR prototype Coated Tablet MRX or MRX1	MR prototype Coated Tablet MRX or MRX1	MR prototype Coated Tablet MRX, MRX1 or MRX2	MR prototype Coated Tablet MRX, MRX1 or MRX2	MR prototype Coated Tablet MRX, MRX1 or MRX2
Unit dose strength(s)/ Dosage level(s):	120 mg / 120 mg (may be changed following review of Part A data)	tbc / tbc					
Route of Administration	Oral with 240 mL water						
Dosing instructions:	1 tablet, on the morning of Day 1 Food status: tbc	xx tablets, on the morning of Day 1 Food status: tbc	xx tablets, on the morning of Day 1 Food status: tbc	xx tablets, on the morning of Day 1 Food status: tbc	xx tablets, on the morning of Day 1 Food status: tbc	xx tablets, on the morning of Day 1 Food status: tbc	xx tablets, on the morning OR evening of Day 1 Food status: tbc

Regimen	G	Н	I (Optional)	J (Optional)	K (Optional)	L	M (Optional)
Packaging and Labelling	100 cc HDPE white bottle labelled as required per country requirement.						
Manufacturer	Quotient	Quotient	Quotient	Quotient	Quotient	Quotient	Quotient

MRX is the formulation selected from Part A. MRX1 and MRX2 are alternative MR formulations that may be investigated from Part A. Tablets in Periods 1 and 2 will be manufactured with apertures. Tablets may be manufactured with or without apertures (i.e., drilled or non-drilled) from Period 3 onwards. Tablets without apertures will be manufactured based on a formulation which has already been dosed.

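### Frel_FE admits evening meals, but its fasted reference can only be a morning dose, so an evening Period 7 ratio would combine meal and time of day (minor)

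*Protocol*

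**What the plan says.** The parameter list in Protocol 10.4.1 gives Frel_FE as the relative bioavailability "of fed (high-fat breakfast or high-fat evening meal, standard breakfast or standard evening meal or delayed meal (30 or 60 minutes) vs fasted". The methods table in the same section describes the food-effect contrast as "MR formulation taken in the fed state (test) vs in the fasted state (reference", estimated from a "mixed effects model with regimen as a fixed effect and subject within sequence as a random effect". Neither entry says at what time of day the reference dose was given.

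The Synopsis and Section 5.1 confine evening dosing to one period: "The single dose may be given in the morning or evening (Part B, Period 7 only". In Section 7.1.2, Part B regimens H to L carry the instruction "xx tablets, on the morning of Day 1" (regimen G is one tablet, also in the morning). Only regimen M reads "xx tablets, on the morning OR evening of Day 1". Section 5.1.2 lets Part B tablets be given fed, fasted, or "administered 30 or 60 minutes before a standard or high-fat (Period 7 only) breakfast/evening meal (Period 7 only". Under Section 5.1.3, the review after Period 6 settles one dosing time and one prandial status for Period 7.

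For the time-of-day ratio, 10.4.1 does hold the other factor fixed. It compares "evening dosing (test) versus morning dosing in the same prandial state (reference".

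**The concern.** A ratio named as a food effect is read as the change produced by the meal with everything else held equal. For an evening meal this design cannot hold everything else equal, because no evening fasted dose exists alongside the evening fed one. The protocol applies the matching principle in one direction only: the time effect is matched on prandial state, but the food effect is not matched on dosing time.

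Section 5.4 presents a changed food regimen and a changed time of administration as two separate things that Period 7 may explore. If both change together and the result is labelled Frel_FE, an effect of clock time is credited to the meal, or a real meal effect is hidden. The 90% confidence interval gives no warning, because it is centred on the combined ratio.

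**Working it through.** The plan states no figure to reproduce, so the check is structural.

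**Inputs**
- Part B is a fixed sequence of up to seven periods (Protocol 5.1.2), with one dose in each inpatient period (Synopsis, Treatment Groups and Duration).
- Periods 1 to 6 are morning only; Period 7 is morning or evening (5.1, 7.1.2).
- Part A participants may not enter Part B (6.2, exclusion 21), and all Part A doses are given in the morning (7.1.1). Part A therefore supplies no within-participant reference and no evening reference.

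**Is an evening fasted reference ever available?** Classify each period as fasted or fed. Periods 1 to 6 give 2^6 = 64 patterns. Setting Period 7 to evening and fed leaves 64 schedules. An evening fasted dose would need a second evening period, and there is none. So 0 of 64 schedules contain one.

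**What the ratio then estimates.** On the geometric-mean scale:

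evening fed / morning fasted = (evening fed / morning fed) × (morning fed / morning fasted) = T × F,

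where T is the time-of-day ratio in the fed state and F is the morning food ratio.

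**Illustration.** The documents give no value for T, so 0.80 to 1.25 is an assumption.
- True F = 1.00 (no food effect): reported ratio 1.00 × 0.80 = 0.80 to 1.00 × 1.25 = 1.25.
- True F = 1.25: reported ratio 1.25 × 0.80 = 1.00 to 1.25 × 1.25 = 1.56.

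Within that range, a time effect could imitate a food effect or cancel one.

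**Can the planned analysis separate T from F?** Not through the model. Evening fed is a single regimen level, so meal and clock time change together. Frel(time effect) supplies T only if the same prandial state, dose and formulation was also given in the morning, and the protocol does not guarantee this. A delayed high-fat meal is allowed in Period 7 only, so an evening dose ahead of such a meal has no morning counterpart. In the SAP's treatment table (Section 5.1), the Part B regimens other than M are fasted or high-fat fed. If M is the Period 7 regimen, as in Protocol 7.1.2, an evening standard or delayed meal would also have lacked a morning match.

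**Is morning fasted a fair stand-in?** Section 6.3.1 requires at least 10 hours of fasting before a morning fasted dose, but at least 4 hours before an evening dose that is fasted or precedes a delayed meal. An evening delayed-meal dose can therefore differ from its morning fasted reference in length of fast as well.

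**The case against.** The strongest reply is that little depends on this definition, and most of that reply stands.

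- Protocol 10.4.1 leaves the detail to the Reporting and Analysis Plan. That plan knows of Period 7 (SAP Section 1), yet its only Part B food-effect comparison is 480 mg high-fat fed against 480 mg fasted (8.1.5.1). No regimen label mentions evening (5.1), and no time-effect ratio is listed (10.6.5). The definition is therefore not carried into any listed comparison.
- The evening-dosing objective in Protocol Section 4 is tied to Frel(time effect) alone, which is matched on prandial state. The objectives that use Frel_FE concern a high-fat breakfast, a standard breakfast and a delayed meal, the last two in Part A.
- Section 5.4 says the aim of Period 7 is to reduce the spread between participants in absorption time after the 480 mg tablet with a high-fat breakfast. A mean ratio to fasted does not answer that, so a mislabelled Frel_FE would not directly corrupt it.

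None of this makes the definition correct. Evening meals are named in it, and the SAP adds no rule requiring the same dosing time.

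Three stronger inferences are tempting. A reader might infer that the trial's food-effect results, including the primary one, are biased. The documents do not support this: the primary objective concerns breakfast, and morning fed against morning fasted is unaffected. A reader might try to state how often the confidence interval would miss the true food ratio. Any such figure is fixed by the assumed T, about which the documents say nothing. A reader might infer that the review after Period 6 should be barred from some evening options. The protocol allows those combinations deliberately, and a labelling problem does not justify restricting the schedule.

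**Conclusion.** The point holds as a minor defect in the protocol's definition of Frel_FE. If Period 7 is dosed in the evening with a meal, the ratio to fasted is a combined meal-and-time effect and should not be called a food effect.

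It matters only if three things occur together: the optional Period 7 is run, it is dosed in the evening, and a meal is part of the regimen. Even then the result is exploratory, and no hypothesis is tested (Protocol 10.1). The size of the bias is unknown. That the structural confounding exists rests on the documents alone; the numerical range rests on the assumed ratio.

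**What to change.** In Protocol 10.4.1:

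1. Restrict Frel_FE to fed/fasted pairs with the same dosing time, dose and formulation, and remove evening meals from its definition. The dosing-time condition also covers an evening dose given before a delayed meal, which deleting the words alone would miss.
2. Report any evening-fed versus morning-fasted ratio under its own name, as a combined meal-and-time effect.
3. Show Frel(time effect) beside it where a morning dose in the same prandial state, dose and formulation exists. Where none exists, say so.

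The cost is a few words, with no new data, participants or analyses. The downside is that an evening regimen could not be reported as a food effect. The SAP's listed comparisons need no change. No limit on which Period 7 schedule may be chosen is proposed.

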6.3. Lifestyle Considerations

6.3.1. Meals and Dietary Restrictions

- Refrain from consumption of red wine, Seville oranges, grapefruit or grapefruit juice, pomelos, exotic citrus fruits, grapefruit hybrids, or fruit juices from Seville oranges and grapefruit derivatives for 24 hours before admission to each study period until after collection of the final PK sample in that period.
- Refrain from consumption of poppy seeds for 48 hours before screening, and from 48 hours before admission to each study period until after collection of the final PK sample in that period.
- For fasted dosing, no water is allowed from 1 hour before dosing until 1 hour after dosing with the exception of the 240 mL water provided with each dose. Water is allowed ad libitum at all other times.
- For fasted dosing, participants will be provided with a light snack on the evening before dosing and will be required to fast from all food and drink (except water) for a minimum of 10 hours before dosing until approximately 4 hours after dosing. Lunch will be provided approximately 4 hours after dosing, an evening meal will be provided approximately 10 hours after dosing and an evening snack will be provided approximately 14 hours after dosing.
- For dosing after a high-fat breakfast or a standard breakfast, participants will be provided with a light snack on the evening of Day -1 and will fast from all food and drink (except water) until the following morning, when they will be provided with the appropriate breakfast. The breakfast should be consumed over a maximum period of 25 minutes, with dosing occurring 30 minutes (±5 minutes, Part B Period 7

only) after the start of breakfast. Participants should be encouraged to eat their meal evenly over the 25 minutes period. It is acknowledged that some participants will take less time to eat, but dosing should still occur 30 minutes after the start of breakfast. Subjects must complete 90% of the meal to be dosed. Lunch will be provided approximately 4 hours after dosing, an evening meal will be provided approximately 10 hours after dosing and an evening snack will be provided approximately 14 hours after dosing.

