- For dosing before a standard meal, participants will be provided with a light snack on the evening before dosing and will be required to fast from all food and drink (except water) for a minimum of 10 hours before dosing. No water is allowed from 1 hour before dosing until 1 hour after dosing, with the exception of the 240 mL water provided with each dose. Water will be allowed ad libitum 1 hour after dosing or after administration of the standard breakfast, whichever is sooner. A standard breakfast will be provided either 30 or 60 minutes after dosing. Lunch will be provided approximately 4 hours after dosing, an evening meal will be provided approximately 10 hours after dosing.
- For evening dosing (Part B Period 7 only):
 - For fasted dosing, participants will be provided with a light snack on the day of dosing (Day 1) and will be required to fast from all food and drink (except water) for a minimum of 4 hours before dosing. No water is allowed from 1 hour before dosing until 1 hour after dosing, with the exception of the 240 mL water provided with each dose. Water will be allowed ad libitum 1 hour after dosing. De-caffeinated fluids will be allowed ad-libitum from 4 hours post-dose. Participants will be provided with a snack at 4 hours post-dose.
 - For dosing before a standard or high-fat meal (delayed meal), participants will be provided with a light snack on the day of dosing (Day 1) and will be required to fast from all food and drink (except water) for a minimum of 4 hours before dosing. No water is allowed from 1 hour before dosing until 1 hour after dosing, with the exception of the 240 mL water provided with each dose. Water will be allowed ad libitum 1 hour after dosing or after administration of the standard or high-fat evening meal (which will contain the same content as the breakfast), whichever is sooner. A standard or high-fat evening meal will be provided either 30 or 60 minutes after dosing. De-caffeinated fluids will be allowed ad-libitum from 4 hours post-dose. Participants will be provided with a snack at 4 hours post-dose.

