 - For dosing after a high-fat or a standard evening meal (which will contain the same content as the breakfast), participants will be provided with a light snack on the day of dosing (Day 1) and will fast from all food and drink (except water), until the appropriate time when they will be provided with the appropriate meal. The meal should be consumed over a maximum period of 25 minutes, with dosing occurring 30 minutes (±5 minutes) after the start of the meal. Participants should be encouraged to eat their meal evenly over the 25 minutes period. It is acknowledged that some participants will take less

time to eat, but dosing should still occur 30 minutes after the start of the meal. Subjects must complete 90% of the meal to be dosed. De-caffeinated fluids will be allowed ad-libitum from 4 hours post-dose. Participants will be provided with a snack at 4 hours post-dose.

- During each dosing session, participants will abstain from ingesting caffeine- or xanthine-containing products (e.g., coffee, tea, cola drinks, and chocolate) for 24 hours before admission until after collection of the final PK sample in that period.
- Participants will abstain from alcohol for 24 hours before screening. During each dosing session, participants will abstain from alcohol from 24 hours before admission until after collection of the final PK sample in that period.
- Current smokers or users of other tobacco products will not be enrolled in this study.

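### For fasted and delayed-meal dosing, the evening-versus-morning contrast mixes time of day with time since food, because the minimum pre-dose fast is 4 h in the evening and 10 h in the morning

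*Protocol*

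**What the plan says.** **The contrast.** Protocol Section 4 lists the impact of evening dosing as an exploratory objective, for optional Part B Period 7 only. Section 10.4.1 says Frel(time effect) will be assessed by comparing AUC(0-inf), AUC(0-t), Cmax and Tmax for "evening dosing (test) versus morning dosing in the same prandial state (reference").

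**The meal rules.** Section 6.3.1 writes separate rules by time of day.

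- *Morning, fasted:* after a light snack the evening before, participants are "required to fast from all food and drink (except water) for a minimum of 10 hours before dosing until approximately 4 hours after dosing".
- *Evening, fasted:* "For fasted dosing, participants will be provided with a light snack on the day of dosing (Day 1"), and they are "required to fast from all food and drink (except water) for a minimum of 4 hours before dosing".
- *Delayed meal:* the morning rule, written for a standard breakfast, repeats the 10 h minimum. The evening rule, for a standard or high-fat meal, repeats the 4 h minimum and the Day 1 snack.
- *Fed, morning:* participants "will fast from all food and drink (except water) until the following morning, when they will be provided with the appropriate breakfast".
- *Fed, evening:* after a Day 1 snack they "will fast from all food and drink (except water), until the appropriate time when they will be provided with the appropriate meal". No minimum duration is given.

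Neither document says what counts as the same prandial state for this contrast, adjusts for fasting time or states the difference as a limitation.

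**The concern.** A ratio described as evening against morning in one prandial state invites the reader to attribute any departure from 1 to time of dosing. That holds only if the state means the same thing in both arms. For two of the three kinds of state, Section 6.3.1 makes it mean different things.

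This matters for the purpose of Period 7. Section 5.4 presents a change of food regimen and a change of dosing time as alternative ways to reduce between-subject variability in absorption time. A fasted or delayed-meal contrast changes both at once, so it cannot show which one acted. The protocol itself gives reason to care about food. The Synopsis rationale says earlier polymer-matrix formulations were susceptible to food effects with a high-fat breakfast, and Sections 3.2 and 5.4 link stomach conditions to release rate.

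**Working it through.** The protocol states no figure for this contrast, so there is nothing to reproduce. The check sets the Section 6.3.1 rules side by side.

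| State | Morning | Evening (Period 7) | Matched? |
|---|---|---|---|
| Fasted: minimum pre-dose fast | 10 h, snack the evening before | 4 h, snack on Day 1 | No |
| Delayed meal: minimum pre-dose fast | 10 h, snack the evening before | 4 h, snack on Day 1 | No |
| Fed: dosing meal | Eaten within 25 min, dose 30 min after its start, 90% eaten | Same content as the breakfast, same three rules | Yes |
| Fed: fast before the meal | Overnight | No minimum stated | Cannot be judged |
| Listed post-dose food | Lunch about 4 h, evening meal about 10 h, plus a snack about 14 h for fasted and fed dosing | Snack at 4 h, nothing later listed | Not as listed |

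**Step 1. Size of the fasting gap.** For fasted and delayed-meal dosing: 10 h − 4 h = 6 h, and 4/10 = 40%. The evening minimum is 6 h shorter, or 40% of the morning minimum. Both figures are minimums, so actual fasts could be closer, but no rule requires them to match. For fed dosing no gap can be computed.

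**Step 2. Can the contrast be formed under one set of rules?** Evening dosing exists only in Period 7. Sections 5.1.2 and 7.1.2 make that a single period dosed in the morning or the evening. A within-study morning reference must therefore come from an earlier period, under the morning rules. The mismatch is built into any fasted or delayed-meal time-effect contrast.

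**Step 3. Does the SAP resolve it?** Section 10.4.1 leaves detail to the analysis plan. SAP Section 1 lists the protocol version that added Period 7. However, Section 2.2 has no evening-dosing objective, Section 5.1 has no regimen labelled as evening, Section 8.1.5.1 has no time-effect contrast, and Section 10.10.7.2 has no table for one. Regimen M is labelled 480 mg fed (standard), with no time of day, and no other standard-fed Part B regimen is listed that could serve as its reference.

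**Step 4. Can a bias be sized?** That needs the food effect for this coated tablet, and the share of it that remains after a snack and a 4 h rather than a 10 h fast. The documents give neither.

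**The case against.** The strongest reply concerns scope. Period 7 was prompted by variability of the 480 mg tablet given with a high-fat breakfast, which is a fed-state question, and in the fed state the dosing meal is matched. A reader might infer from the differing rules that the two arms can never share a prandial state. The documents do not support that: meal content, eating time, dosing interval and completion rule agree. This part of the reply stands and limits the point to fasted and delayed-meal dosing.

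The second reply is that the mechanism may be weak. The food-effect statement concerns earlier matrix formulations, and the same rationale says the coating has shown robustness to food in other products and is meant to control release in the stomach. Nothing says that a light snack at least 4 h before dosing acts like part of a high-fat meal. The protocol also attributes faster release to the fed stomach and/or to longer retention when fasted, so even the sign is open. This stands against any claimed size or direction. It does not make the two fasted conditions the same, and robustness to food is what the study is testing.

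Third, the listed evening food stops at a 4 h snack. A reader might infer that no later food is given. The rules do not prohibit it, and the stay runs to 48 h, so this may be only a drafting gap.

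Fourth, the objective can be read as the effect of the evening regimen as given, meals included. That is a reasonable aim, but it does not fit the same-state wording in Section 10.4.1.

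**Conclusion.** The point holds for fasted and delayed-meal dosing. As written, Section 10.4.1 would credit time of day with a difference that also reflects time since food. The mismatch is a 6 h shorter minimum fast, and it rests only on the text of Sections 6.3.1 and 10.4.1.

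For fed dosing it reduces to two smaller differences: the unstated fast before the evening meal and the listed post-dose food.

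A reader might infer that a misleading time-of-dosing ratio will be reported, or that it will be biased upward by a known amount. Neither follows. The SAP plans no such contrast, and the documents contain no figure from which size or sign could be derived. With an exploratory objective in an optional period, the practical impact is limited. The protocol still promises an estimate under a description that its own meal rules contradict, and that is worth correcting.

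**What to change.** Reconcile Section 6.3.1 with Section 10.4.1 in one of two ways.

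1. Limit Frel(time effect) to the fed state, where the dosing meal is matched, and state the remaining differences in prior fast and listed post-dose food.
2. For fasted and delayed-meal dosing, remove the same-prandial-state wording and report the ratio as an evening-regimen effect, meaning time of day plus different food timing, rather than a pure time-of-dosing effect.

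If the contrast is analysed, carry the same definition and label into SAP Sections 2.2 and 8.1.5.1 and the list of displays. If it is not, the SAP should say so.

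The cost is wording and a narrower claim, with no added participants, periods or samples. Aligning the meal schedules themselves would be a clinical and logistic decision with a larger cost. Which fasting rule applies is for the sponsor to decide, and this point does not depend on that choice.
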